#### **5.2 STUDY DRUG**

TPOXX will be supplied as 200-mg capsules containing tecovirimat monohydrate as the active pharmaceutical ingredient. The matching TPOXX placebo will be identical in appearance and have the same excipient ingredients but will not include the active compound. TPOXX capsules are immediate release, size 0, orange and black, hard gelatin capsules containing white to off-white powder. All inactive ingredients/excipients are generally recognized as safe and are United States Pharmacopeia/National Formulary grade. The TPOXX excipients are shown in [Table 5-1](#).

**Table 5-1** Excipients of TPOXX and Matching TPOXX Placebo Capsules

A horizontal bar chart comparing the length of various components against their quality designation. The x-axis represents the length of the components, and the y-axis lists the components. The quality designation is indicated by the length of the bars.

Component	Quality Designation
Component 1	High
Component 2	Medium
Component 3	Medium
Component 4	Medium
Component 5	High
Component 6	Medium
Component 7	Medium
Component 8	Medium
Component 9	Medium
Component 10	Medium

Abbreviations: EP, European Pharmacopeia; JP, Japanese Pharmacopeia; NF, National Formulary; USP, United States Pharmacopeia.

(a) Microcrystalline cellulose and croscarmellose sodium are added as intragrannular and extragrannular excipients.

(b) Removed during processing.

Compendial components are tested and released in accordance with full compendial methods and specifications before their use in clinical formulations. TPOXX 200-mg capsules are manufactured and analyzed for clinical use in accordance with Current Good Manufacturing Practices.

TPOXX capsules are manufactured by:

Further information on TPOXX can be found in the TPOXX Investigator Brochure and Full Prescribing Information.

## 5.2.1 Study Drug Packaging, Preparation, Administration, and Storage

SIGA will be responsible for providing the investigator and clinical investigative sites with adequate quantities of TPOXX and TPOXX matching placebo.

TPOXX capsules and the matching placebo capsules are packaged, labeled, distributed, and placed on stability testing in accordance with Current Good Manufacturing Practice and International Council for Harmonisation (ICH) guidelines.

Packaging of bulk TPOXX:

[REDACTED]

Packaging of bulk matching placebo:

[REDACTED]

Labeling, storage, and distribution of TPOXX and matching placebo:

[REDACTED]

The 28-day supply of 200-mg TPOXX capsules and matching placebo capsules are supplied in 75-mL, high-density polyethylene bottles fitted with a heat induction seal and child-resistant screw cap closure system. Each bottle of TPOXX and matching placebo will contain 42 capsules and will be labeled with at a minimum, the study number, bottle content, direction for distribution, storage conditions, and cautionary statement. The study drug will be provided to subjects in either 4 bottles (subjects weighing 120 kg or less) or 6 bottles (subjects weighing more than 120 kg) containing 42 capsules each. Each daily dose is 3 capsules taken orally either BID or TID depending on the subject's weight, for a total of 6 capsules (1200 mg) or 9 capsules (1800 mg) per day.

TPOXX and matching placebo must be stored in a secure area (e.g., a locked cabinet), out of reach of children and pets, protected from moisture and light, and stored at room temperature (15°C to 30°C or 59°F to 86°F).

TPOXX and matching placebo should not be refrigerated or used beyond the expiration dates provided by the manufacturer.

Clinical investigative sites will be required to keep temperature logs to establish a record of compliance for study drug storage conditions for TPOXX and matching TPOXX placebo.

## **5.2.2 Study Drug Accountability**

The clinical investigative sites will maintain accurate records of receipt of all study drugs, including dates of receipt. Accurate records will be kept regarding when and how much study drug is dispensed and used by each subject in the study. Reasons for departure from the expected dispensing regimen must also be recorded. At the completion of the study, and to satisfy regulatory requirements regarding study drug accountability, all study drug will be reconciled and returned for destruction according to the instructions provided by SIGA.

Each clinical investigative site will maintain a study drug accountability log of all study drug dispensed and returned. Subjects will be instructed to bring the subject diary and all study drug bottles (including empty bottles) and unused study drug (in study drug bottles) with them to every study visit. Study drug for each subject will be inventoried and accounted for by the designated study personnel throughout the study. Study drug accountability will be recorded in the subject's source documentation, entered in the eCRF, and reviewed by the monitor during monitoring visits. On a regular basis and after study completion or termination of the study, the monitor will prepare used and unused study drug bottles for return and destruction.

## **5.3 METHOD OF ASSIGNING SUBJECTS TO TREATMENT GROUPS**

Randomization will be performed using an interactive web response system (IWRS). The randomization will be balanced by using permuted blocks of an appropriate size and be stratified by age group (18 to 30 years, 31 to 45 years, 46 to 64 years, and 65 to 80 years). In the event of the withdrawal of a clinical investigative site, no adjustments to the randomization scheme will be implemented because site will not be used as a stratification factor. After a randomization number has been assigned, it will not be reused.

The PK subset of 40 subjects will be enrolled at up to 2 sites with at least 32 subjects who will receive TPOXX and at least 8 subjects who will receive placebo. Of the remaining subjects who are not enrolled in the PK subset, at least 324 subjects will be randomly assigned to receive TPOXX and 81 subjects to receive placebo. The IWRS will facilitate the random assignment of treatment for subjects in the study. Randomization will occur before study drug administration on Day 1, after it has been confirmed that the subject fulfills all eligibility criteria. The IWRS will assign a randomization number that is used to link the subject to 1 of the 2 treatment groups using a 4:1 ratio based on a computer-generated central randomization schedule prepared before enrollment. The IWRS will also specify the study

drug bottle numbers to be assigned to the subject where the study drug bottle numbers match the treatment group assigned by the randomization list. The assigned study drug bottles will be dispensed to the subject by the clinical investigative site. The randomization code will not be broken or made available to study subjects or their families, investigators, clinical personnel, or site managers until all subjects have completed the double-blind phase of the study and the database has been closed in accordance with the clinical investigative sites standard operating procedures (SOPs).

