**Study Population:**

Adult subjects from 18 to 80 years old, inclusive, are eligible for this study. A total of at least 445 subjects will be enrolled and randomly assigned into stratified age groups (18 to 30 years, 31 to 45 years, 46 to 64 years, and 65 to 80 years). Approximately 356 subjects will be randomly assigned to receive active drug (TPOXX 600 mg) and 89 subjects will be randomly assigned to receive placebo. Overall, across all clinical investigative sites, a goal of approximately 20% of subjects (i.e., 89 subjects) or more will be enrolled and randomly assigned in each age group to ensure a representative investigation of the safety and PK across age groups.

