## **3. STUDY DESIGN**

This is a Phase 3, multicenter, double-blind, randomized, placebo-controlled study to assess the safety, tolerability, and PK of oral TPOXX 600 mg when administered for 28 days in adult subjects.

A total of at least 445 subjects (includes a PK subset of 40 subjects), ages 18 to 80, inclusive, will be enrolled and randomly assigned within stratified age groups (18 to 30 years, 31 to 45 years, 46 to 64 years, and 65 to 80 years) to 1 of 2 treatment groups in an overall randomization of 4:1 (approximately 356 subjects will receive TPOXX and 89 subjects will receive TPOXX matching placebo). There will be 2 dosing regimens based on the subjects body weight: subjects with a body weight of 120 kg or less will be administered either TPOXX 600 mg or placebo BID, 12 hours apart ( $\pm$ 30 minutes); and subjects with a body weight of more than 120 kg will be administered TPOXX 600 mg or placebo TID, 8 hours apart ( $\pm$ 30 minutes). The enrollment goal for the study is to randomly assign a sufficient number of subjects to ensure that at least 300 subjects receive at least 92% of the oral TPOXX 600 mg BID or TID dosing regimen over the 28-day treatment period. Overall, across all clinical investigative sites, a goal of approximately 20% of subjects (i.e., 89 subjects) or more will be enrolled and randomly assigned in each age group to ensure a

representative investigation of TPOXX safety and PK across age groups. The treatment groups will be as follows:

- Treatment Group 1: An oral dose of 600 mg (3 × 200-mg capsules) TPOXX BID (every 12 hours [ $\pm$ 30 minutes]) for subjects with a body weight of 120 kg or less or TID (every 8 hours [ $\pm$ 30 minutes]) for subjects with a body weight more than 120 kg for 28 days (Day 1 to Day 28).
- Treatment Group 2: An oral dose of placebo (3 capsules identical to TPOXX) BID (every 12 hours [ $\pm$ 30 minutes]) for subjects with a body weight of 120 kg or less or TID (every 8 hours [ $\pm$ 30 minutes]) for subjects with a body weight more than 120 kg for 28 days (Day 1 to Day 28).

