## **6.1 PHARMACOKINETIC SUBSET ASSESSMENTS AND ENDPOINTS**

Blood samples for PK analysis of TPOXX in plasma will be collected at the time points specified in the schedule of events ([Table 9-1](#)).

The following plasma PK parameters will be calculated separately for BID or TID dosing as endpoints for TPOXX to the extent that data permit using actual sampling times rather than scheduled sampling times and will include, but are not limited to the following:

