## **3. Study Design and Description**

This is a Phase 3, multicenter, double-blind, randomized, placebo-controlled study to assess the safety, tolerability, and PK of oral TPOXX 600 mg when administered for 28 days in adult subjects.

A total of at least 445 subjects (includes a PK subset of 40 subjects), ages 18 to 80, inclusive, will be enrolled and randomly assigned within stratified age groups (18 to 30 years, 31 to 45 years, 46 to 64 years, and 65 to 80 years) to 1 of 2 treatment groups in an overall randomization of 4:1 (approximately 356 subjects will receive TPOXX and 89 subjects will receive TPOXX matching placebo). There will be 2 dosing regimens based on the subject's body weight: subjects with a body weight of 120 kg or less will be administered either TPOXX 600 mg or placebo two times a day (BID), 12 hours apart ( $\pm$ 30 minutes); and subjects with a body weight of more than 120 kg will be administered TPOXX 600 mg or placebo three times a day (TID), 8 hours apart ( $\pm$ 30 minutes). The study will consist of a screening period (Day -28 to Day -2), 1 check-in, on-site visits (Day 7, Day 14, and Day 21), a dosing complete/ET visit (Day 29), and 2 follow-up telephone calls (Day 42 [+2 days] and Day 58 [+2 days]). The total duration of the study for each subject, including screening, treatment, and follow-up telephone calls will be approximately 86 days,

The enrollment goal for the study is to randomly assign a sufficient number of subjects to ensure that at least 300 subjects receive at least 92% of the oral TPOXX 600 mg BID or TID dosing regimen over the 28-day treatment period. Overall, across all clinical investigative sites, a goal of approximately 20% of subjects (i.e., 89 subjects) or more will be enrolled and randomly assigned in each age group to ensure a representative investigation of TPOXX safety and PK across age groups. The treatment groups will be as follows:

- Treatment Group 1: An oral dose of 600 mg (3 × 200-mg capsules) TPOXX BID (every 12 hours [ $\pm$ 30 minutes]) for subjects with a body weight of 120 kg or less or TID (every 8 hours [ $\pm$ 30 minutes]) for subjects with a body weight more than 120 kg for 28 days (Day 1 to Day 28).

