### **Pooling of Sites**

Up to 10 sites in the USA will be used in this study. The PK subset will be enrolled at 1 Phase 1 unit. For the remaining sites, a maximum number of subjects will be agreed upon and enrollment

will be competitive. Thus major differences in subject enrollment numbers per site are not expected, and therefore there will be no inter-subject pooling of data.

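### The PK subset is filled without regard to body weight, so the separately planned TID (over 120 kg) PK endpoints may rest on too few treated subjects to describe

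*Combined protocol and SAP*

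**What the plan says.** Protocol 5.3 sets the composition of the subset: "The PK subset of 40 subjects will be enrolled at up to 2 sites with at least 32 subjects who will receive TPOXX", with at least 8 more on placebo. The IWRS is to "link the subject to 1 of the 2 treatment groups using a 4:1 ratio", stratified by age group only. Site is expressly not a stratification factor, and neither body weight nor dosing regimen is named as one. SAP 4, Pooling of Sites, gives a different site count: "The PK subset will be enrolled at 1 Phase 1 unit".

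Protocol 6.1 then states: "The following plasma PK parameters will be calculated separately for BID or TID dosing as endpoints for TPOXX", qualified as being done as far as the data allow. Protocol 7.3.1 and SAP 8.1 and 8.3 summarise concentrations and parameters by dosing regimen and plot mean profiles by regimen. The SAP's index of listings has a TID-only listing of individual parameters (16.2.6.3).

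On age, Protocol 3 sets "a goal of approximately 20% of subjects (i.e., 89 subjects) or more will be enrolled and randomly assigned in each age group", counted over all sites. SAP 3 gives the purpose as "to ensure a representative investigation of TPOXX safety and PK across age groups", and the Study Population paragraph of the Synopsis says much the same.

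Neither document gives a minimum or target number of subjects over 120 kg, in the subset or in the whole trial.

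**The concern.** Describing the 28-day PK profile is the secondary objective, and TID is one of the two regimens for which it is to be described. It carries the higher daily dose (1800 mg against 1200 mg, Protocol 5.2.1). Full profiles come only from the PK subset. Outside it, the only concentration taken is a single sample from a subject who discontinues, if the early termination visit falls within 30 hours of the last dose (Protocol 4.4.2). That cannot give a profile.

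How many TID subjects are sampled is therefore left to whoever presents at one or two sites. With none there is no TID profile. With one, the SD and CV are undefined. With two, they rest on a single degree of freedom. A by-regimen table cannot recover subjects who were never sampled, and the trial would in effect describe PK for BID only.

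The age statement raises a lesser question: a goal counted over all 445 subjects is said to secure PK information that comes from 40 of them.

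**Working it through.** **1. The plan's own split.** At 4:1, 40 × 4/5 = 32 and 40 × 1/5 = 8. The other 405 give 324 and 81. The totals are 32 + 324 = 356 and 8 + 81 = 89, as stated. The arithmetic of the subset is sound; what is missing is a rule on who fills it.

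**2. TPOXX subjects on TID.** Inputs: n = 32 treated (Protocol 5.3), and p, the share of PK-subset subjects over 120 kg. The documents do not give p, so it is an assumption varied from 2% to 20%. With X binomial (32, p):

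P(X ≤ 2) = (1−p)^32 + 32p(1−p)^31 + 496p²(1−p)^30

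At p = 0.05 this is 0.194 + 0.326 + 0.266 = 0.786.

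**3. Evaluable subjects.** The PK Population requires at least 92% of doses (Protocol 7.2). If the design's own ratio, 300/356 = 0.843, is assumed to apply to the subset, 32 × 0.843 = 27 remain.

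| Assumed share over 120 kg | Expected of 32 | P(none of 32) | P(0–2 of 32) | P(0–2 of 27) |
|---|---|---|---|---|
| 2% | 0.6 | 0.52 | 0.97 | 0.98 |
| 5% | 1.6 | 0.19 | 0.79 | 0.85 |
| 10% | 3.2 | 0.03 | 0.37 | 0.48 |
| 15% | 4.8 | 0.01 | 0.12 | 0.21 |
| 20% | 6.4 | 0.001 | 0.03 | 0.07 |

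P(0–2) crosses one half at a share of 8.3% with 32 subjects and 9.8% with 27.

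**4. Age groups.** If the subset mirrored the 20% goal, each group would expect 32 × 0.20 = 6.4 treated subjects, and P(0–2) for a given group would be 0.03. If the PK site drew only 10% or 5% from one group (assumed), P(0–2) would be 0.37 or 0.79. But PK is summarised by study day and regimen only; the SAP's table index has demographics by age for the PK Population and no PK summary by age.

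**5. What a target would give.** Eight subjects over 120 kg give 8 × 0.8 = 6.4 on TPOXX and 6.4 × 0.843 = 5.4 evaluable. Since weight is not a stratum, the split within TID is not guaranteed: P(at least 6 of 8 on TPOXX) is about 0.80. Without targeted recruitment, finding 8 takes about 8/p eligible subjects: 400 / 160 / 80 at shares of 2 / 5 / 10%.

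**6. Cost to BID.** Moving 6 of 32 places to TID leaves 26 and raises the BID standard error by √(32/26) = 1.11. As an illustration only, with an assumed between-subject CV of 40%, a 95% interval for a geometric mean widens from a factor of about 1.15 to about 1.17 either way.

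**The case against.** The best defence is that the plan already allows for sparse TID data. The objective is to describe PK in adults, with no TID-specific objective and no precision claim. Parameters are derived only as far as the data allow, and individual TID values have their own listing. That lowers the harm, but it sets no minimum number and does not say that TID may go undescribed, while SD, CV and geometric statistics are still planned by regimen.

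The low counts also depend wholly on an assumed weight share. At 15 to 20% the problem is unlikely, and nothing in the documents favours 5% over 15%. This stands and limits the conclusion. PK-site instructions or IWRS specifications, which are not part of these documents, might set a target.

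A firm quota would be hard to meet. The whole trial is 445 subjects over about 12 sites (Protocol 4) or up to 10 (SAP), roughly 37 to 45 per site, against the 80 to 400 eligible subjects found in step 5. This also stands.

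Three stronger readings should be resisted. A reader might infer that the age groups face the same problem as TID; they do not, because no planned PK output is by age and about 6 treated per group are expected if the subset follows the goal. A reader might infer that TID subjects have the higher plasma exposure; the documents give only a higher daily dose, adjusted for body weight. And a reader might judge the TID summary by the width of a confidence interval, but none is planned for the PK parameters.

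**Conclusion.** The concern holds for TID. The plan makes TID PK parameters separate endpoints but has no enrolment rule that would supply the subjects. Whether 0 to 2 treated TID subjects is likely depends on an unstated weight share: more likely than not below about 8% (about 10% if only 27 are evaluable), and improbable at 20%. The documents do not show that the shortfall will occur, only that nothing guards against it.

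For age, the point is one of wording: the stated assurance about PK has neither an enrolment rule in the subset nor a planned output behind it.

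The BID profile and the primary safety objective are unaffected. This is a worthwhile, inexpensive improvement, not a flaw in the trial's main purpose.

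**What to change.** (a) In Protocol 5.3 and the IWRS or PK-site instructions, keep the subset at 40 but offer PK places first to eligible subjects over 120 kg; weight is already measured at screening. Use a soft target, for example about 8 enrolled, giving about 6 on TPOXX and about 5 evaluable. It should not be a hard quota that holds up enrolment.

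(b) In the SAP, state that if fewer than 3 evaluable TPOXX subjects are on TID, their data are given as individual listings only, and the report says that the TID PK profile was not characterised. The cut-off of 3 is a judgement.

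(c) Either apply the age goal within the PK subset and add a PK-by-age summary, or remove PK from the statement about age groups wherever it appears: both places in the Synopsis (study design and Study Population), Protocol 3 and SAP 3.

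(d) Reconcile the number of PK sites between Protocol 5.3 and SAP 4.

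Cost: no added subjects, visits or samples, unless the age goal is applied within the subset and itself slows recruitment. PK-site recruitment may be slower under (a), the target may still be missed, and BID precision falls slightly. Part (b), the deletion option in (c), and (d) cost only wording.

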## **5.4 BLINDING**

### **5.4.1 Blinding Procedures**

This study will be performed as a double-blind study. All parties involved in the study except for the medical monitor (in the event of a suspected unexpected serious adverse reaction) and the unblinded statistician for DSMB Closed Session meetings, will remain blinded to the treatment until study completion. Under routine circumstances, the blind will not be broken.

TPOXX and matching placebo capsules are indistinguishable and all study drug bottles will be packaged the same way. Study drug bottle labeling will include all required identifying information except for the identity of the study treatment.

### **5.4.2 Breaking the Blind**

The medical monitor will be responsible for maintaining the blind throughout the study. If a subject becomes seriously ill or pregnant during the study, the blind will be broken only if knowledge of the administered study drug will affect that subject's available treatment options. In the event of a medical emergency requiring identification of the study drug administered to an individual subject, the investigator will make every attempt to contact the medical monitor to explain the need for opening the code within 24 hours of unblinding the subject's randomization assignment. The investigator will be responsible for documenting the time, date, reason for the code break, and the names of the personnel involved. All unblinding activities will be tracked via an audit trail in IWRS. Requests for unblinding of a subject's randomization assignment will be made through the IWRS after consultation with the medical monitor. Subject code breaks by the investigator will result in withdrawal of the subject from the study. The date, time, and reason for the unblinding must be documented on the appropriate page in the eCRF, and SIGA must be informed as soon as possible. The treatment assignment of subjects will remain blinded until all clinical evaluations have been completed. Unblinding at the end of the study will occur only by written request from the

lead statistician to the unblinded randomization statistician and the unblinded IWRS team after database lock and confirmation of protocol deviations. The DSMB may request to unblind the treatment assignment of a subject or the study at any time.

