## **4.4 WITHDRAWAL OF SUBJECTS FROM THE STUDY**

### **4.4.1 Reasons for Withdrawal**

Under certain circumstances, a subject may be terminated from participating in the study based on the opinion of the investigator, SIGA, FDA, and/or the Data Safety Monitoring Board (DSMB). Subjects will be withdrawn from the study if they do not meet the study inclusion and exclusion criteria before dosing of the study drug.

Subjects can withdraw consent and discontinue from the study at any time, for any reason, without prejudice to further treatment.

The investigator may withdraw a subject from the study for any of the following:

- Subject is in violation of the protocol.
- Subject experiences a serious or intolerable AE that in the investigator's opinion requires withdrawal from the study.
- Subject becomes pregnant.
- Subject is noncompliant.
- Subject has laboratory abnormalities for assessments listed in [Sections 4.1](#) or [Section 4.2](#) that meet grade 3 or grade 4 on the Division of Acquired Immune Deficiency Syndrome AE Grading Table; any other grade 3 or grade 4 AE; or a grade 2 or higher rash considered by the investigator to be possibly, probably, or definitely related to study drug.
- Subject develops, during the course of the study, symptoms or conditions listed in the exclusion criteria.

- Subject develops during the course of the study, laboratory abnormalities listed in the exclusion criteria.
- Subject requires a medication prohibited by the protocol.
- Subject requests an early discontinuation for any reason.
- Subject's primary care provider requests that the subject be withdrawn.
- The FDA, SIGA, or the DSMB requests subject withdrawal based on study safety findings.

The investigator can also withdraw a subject upon the request of SIGA or if SIGA terminates the study. Upon occurrence of an SAE or intolerable AE, the investigator will confer with the medical monitor and with SIGA. If a subject is discontinued because of an AE, the event will be followed until it is resolved or stabilized as determined by the investigator and/or the medical monitor.

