#### **4.4.2 Handling of Withdrawals**

Subjects are free to withdraw from the study at any time upon request. Subject participation in the study may be stopped at any time at the discretion of the investigator or at the request of SIGA.

When a subject withdraws from the study, the reason(s) for withdrawal will be recorded by the investigator in the electronic case report form (eCRF). Whenever possible, any subject who withdraws from the study prematurely will undergo all ET visit assessments ([Table 9-1](#) and [Table 9-2](#)). A blood sample will be collected for all subjects who discontinue from the study for TPOXX plasma concentration analysis *if the ET visit occurs within 30 hours after the subject's last dose of TPOXX/matching placebo* in order to collect information about the relationship between TPOXX blood level and ET from the study. Any subject who fails to return for final assessments will be contacted by the site in an attempt to have them comply with the protocol. The status of subjects who fail to complete final assessments will be documented in the eCRF.

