### **6.2.1.8                   Reporting of Pregnancy**

Pregnant women are not eligible to participate in the study. Subjects must be counseled regarding prevention of pregnancy and encouraged to make every effort to avoid pregnancy during study participation. If a subject becomes pregnant during study participation, study drug dosing will be discontinued, and the subject will be withdrawn from the study. The pregnancy itself is not considered an SAE. However, the investigator must complete the pregnancy report form and fax it to PPD Pharmacovigilance within 24 hours of knowledge of the pregnancy. After delivery or termination of pregnancy, the follow-up pregnancy report form should be completed and submitted via fax to PPD Pharmacovigilance. Spontaneous abortion should always be reported as an SAE. Pregnancy data will be captured and followed by PPD. All pregnancies and outcomes will be tracked by PPD Pharmacovigilance. A pregnancy case will not be closed until after the child is followed for 3 months.

If there are complications during the pregnancy, the complications will be recorded as AEs in the usual manner. The subject will be asked to report the outcome of the pregnancy. If there is a congenital anomaly, this will be recorded as an SAE in the data forms for the mother (i.e., the study subject).

If a subject becomes pregnant during the study after receiving the study drug, all safety evaluations will be collected as per protocol. In addition, at the time that the pregnancy is reported, consent will be requested to contact the subject and her physician in the postpartum period to assess delivery and health status of the neonate.

If the partner of a male subject becomes pregnant, the partner will be asked for consent to allow her treating physician to provide SIGA or its designee with follow-up information regarding the pregnancy and its outcome.

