### **5. Subject Disposition**

#### **5.1. Disposition**

A disposition table will be provided by treatment for the number and percentage of subjects enrolled/randomized, completed, and discontinued together with the reasons for discontinuation. This table will also include the number and percentage of subjects recruited into each age group (randomization strata) and the number and percentage of subjects included in each analysis population will also be presented.

Informed consent, eligibility, and randomization details and protocol details will be listed for all enrolled subjects.

The following will be summarized for the overall population and by treatment for all subjects.

- The number of subjects who were enrolled
- The number of subjects who were randomized
- The number of subjects who received each treatment
- The number of subjects who completed the study treatment
- The number of subjects who did not complete the study treatment
- The number of subjects who completed the study
- The number of subjects who did not complete the study (both overall and according to reasons for discontinuation from the study)
- The number of subjects in each analysis population

Subject disposition will be summarized by dose level and overall based on ITT population using frequency distribution or descriptive statistics. Subjects who complete, withdraw consent, or are terminated early from the study and the associated reasons will be summarized using frequency distribution.

Baseline demographic and background variables will be summarized by treatment for the ITT, Safety, PP Safety, and PK Populations. The demographics table will also be summarized overall

and by age group as per the stratification used in randomization. For treatment-related tables and listings, the data will be summarized by BID or TID study drug dosing regimen.

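### An investigator code break forces withdrawal from the study and so ends the remaining on-site safety visits for safety-relevant subjects

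*Combined protocol and SAP*

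**What the plan says.** Protocol 5.4.2 and SAP 4.3 carry the same sentence: "Subject code breaks by the investigator will result in withdrawal of the subject from the study". It is mandatory, and it refers to the study rather than to study drug.

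Two occasions for unblinding an individual subject are given in the same paragraph:
- "In the event of a medical emergency requiring identification of the study drug administered to an individual subject"
- "If a subject becomes seriously ill or pregnant during the study, the blind will be broken only if knowledge of the administered study drug" would affect that subject's treatment options.

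For a subject who leaves early, protocol 4.4.2 provides that, so far as possible, "any subject who withdraws from the study prematurely will undergo all ET visit assessments", and it treats these as the final assessments. Other follow-up continues:
- An AE that led to discontinuation is followed until it resolves or is stable (4.4.1, 6.2.1).
- SAEs are collected for 30 days after the last dose (6.2.1.4).
- Section 3 promises every subject two telephone calls.

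The documents know the difference between leaving treatment and leaving the study. SAP 5.1 tabulates "The number of subjects who did not complete the study treatment" separately from study non-completion. For pregnancy, protocol 6.2.1.8 names both acts: "study drug dosing will be discontinued, and the subject will be withdrawn from the study". The same section then says that after a pregnancy "all safety evaluations will be collected as per protocol".

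**The concern.** The primary objective is safety and tolerability. The people most likely to be unblinded by an investigator are those with an acute medical problem on study. Under the rule as written, the scheduled laboratory tests, ECGs, vital signs and examinations stop for exactly these people after one ET visit. Neither the protocol nor the SAP describes a way to remain in the study after a code break.

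Two features of the analysis add to this. Under SAP Section 4, unscheduled results are left out of summary tables except when they set the baseline. Repeat laboratory or ECG results obtained while following the event would therefore appear in listings only. No exception is made for the table of maximum post-baseline toxicity grade. Also, time to withdrawal for any reason (SAP 9.3.2) will count each code break as an event because the protocol requires the withdrawal, whether or not the subject would otherwise have left.

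**Working it through.** **1. The plan's own figure.** Protocol 7.1 gives about 95% probability of seeing at least one AE of 1% incidence in 300 TPOXX subjects. Check: 1 − 0.99^300 = 0.951, so it reproduces. The documents give no code-break rate. Assume that 0 to 10 of the 300 are lost entirely:

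| Lost | Probability |
|---|---|
| 0 | 95.1% |
| 1 | 95.0% |
| 3 | 94.9% |
| 5 | 94.8% |
| 10 | 94.6% |

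The design figure barely moves. The issue is which data are lost, not power.

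**2. Scheduled visits lost.** The post-dose on-site visits are Days 7, 14, 21 and 29 (protocol Section 3). Visits forgone are those later than the day of the code break. One ET visit, if held, replaces one of them.

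| Day of code break | Visits forgone | Number | Net of ET visit |
|---|---|---|---|
| 3 | 7, 14, 21, 29 | 4 | 4 − 1 = 3 |
| 10 | 14, 21, 29 | 3 | 3 − 1 = 2 |
| 17 | 21, 29 | 2 | 2 − 1 = 1 |
| 24 | 29 | 1 | 1 − 1 = 0 |

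If the ET visit cannot be held, the loss is the third column.

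**3. Telephone calls.** Section 3 places the calls 14 and 30 days after the last dose and equates them with Day 42 and Day 58. The two agree only for a last dose on Day 28 (28 + 14 = 42; 28 + 30 = 58). For a last dose on Day 14 they fall on Day 28 (14 + 14) and Day 44 (14 + 30), which is 14 days earlier than the fixed days. The calls are promised to all subjects, yet 4.4.2 treats the ET assessments as final. The documents do not say which timing applies to a subject withdrawn after a code break, or whether that subject is called at all.

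**4. Pregnancy.** In 6.2.1.8 the subject is withdrawn, yet all safety evaluations continue under the protocol. Both cannot hold in the ordinary sense of withdrawal from the study. In addition, 4.4.1 lists pregnancy among reasons for which the investigator may withdraw a subject, whereas 6.2.1.8 makes withdrawal mandatory.

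**The case against.** The strongest reply is that little is lost, and much of it stands.

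- **Safety follow-up does not end.** The event is followed to resolution or stability, SAEs are collected for 30 days after the last dose, and calls are promised to everyone. What ends is the scheduled on-site visits.
- **The primary endpoint is nearly untouched.** The AE rate counts subjects with at least one post-dose AE (SAP 4.5.1, 9.3). A subject unblinded for an emergency or serious illness after dosing will normally already be counted. A reader might infer informative loss in the primary AE rate; the documents do not support that.
- **Time to withdrawal is explicitly for any reason**, and reasons for discontinuation are tabulated. The endpoint is therefore not mis-specified. The remaining point is that some of its events are produced by the rule itself.
- **The scope is narrow.** The consequence is stated for code breaks by the investigator. None is stated for unblinding by the medical monitor or at the DSMB's request.

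Two further readings are tempting and fail. One is that the same compulsory exit applies to every reason in 4.4.1. That section says "The investigator may withdraw a subject from the study for any of the following", which is discretionary, and 5.5.2.2 leaves prohibited medication to a joint decision by investigator and sponsor. The other is to size the problem from the gap between 356 randomised to TPOXX and the target of 300, which is 56, or 56/356 = 15.7%. That gap is a margin for receiving at least 92% of doses. It is neither a withdrawal rate nor a code-break rate.

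The reply does not restore the scheduled data. Off-schedule results stay out of the summary tables, and a telephone call yields no laboratory or ECG result.

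**Conclusion.** The point holds in a narrow form. An investigator code break removes the subject from the study, and up to 3 scheduled on-site safety visits are lost net of an ET visit (4 if no ET visit takes place). The loss falls on later laboratory, ECG, vital-sign and AE data from safety-relevant subjects. The primary AE rate and the 95% detection figure are little changed.

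This rests on three assumptions: code breaks are few, since no rate is given; withdrawal carries its ordinary meaning, so that scheduled visits lapse; and the SAP rule on unscheduled results is applied as written. More loss in one arm than the other would follow only if that arm had more code breaks, which cannot be known in advance. The conflicts over pregnancy and call timing are wording faults that need correcting in any case.

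**What to change.** - **Code break (protocol 5.4.2 and SAP 4.3).** Replace withdrawal from the study with continued participation in the remaining scheduled safety visits and both telephone calls, unless the subject withdraws consent. Flag the subject as unblinded in the analysis data.
- **Study drug.** The sponsor must state separately what happens to dosing after a code break. The current text ends it only by ending participation. No rule is proposed here.
- **Analysis.** Report study withdrawal and study-drug discontinuation separately, including in the time-to-event analysis of SAP 9.3.2.
- **Pregnancy.** Reconcile the two statements in 6.2.1.8 with each other and with 4.4.1.
- **Calls.** State, for subjects who stop early, whether the calls are timed from the last dose or fixed at Day 42 and Day 58, and confirm that withdrawn subjects are called.

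The cost is wording in both documents plus a few visits per affected subject that are already in the schedule. The downside is that AE reports after the code break are no longer blinded. The flag lets those reports be identified and, if wanted, set aside in a sensitivity analysis.
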